10.4 Data analyses and Presentations

A full statistical analysis plan will be developed before the final analysis. It will be based on the following summary:

10.4.1 Participant Populations

- Intention-to-treat (ITT) population: all participants randomised and given at least one immunisation in the trial.
- Replacement participant population: participants who were not randomised but did receive at least one immunisation.
- Per-protocol (PP) population: all participants randomised and non-randomised who were immunised with all scheduled immunisations, and who complete the trial.

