7. ASSESSMENTS AND FOLLOW-UP

7.1 Duration of Follow-up and Schedule

The assessments that will be performed at each visit are described in **Table 5**.

Participants will be required to make a minimum of 11 scheduled outpatient visits over the course of up to 30 weeks. Time 0 will start on the day of enrolment, which is also the day of randomisation and first immunisation.

Screening can take place up to 6 weeks (42 days) before time 0.

Immunisations will take place at weeks 0, 4, 8 and 20.

A 12th scheduled outpatient visit, at Week 44, will only take place for participants known to have responded to the vaccine.

Serum will be collected for immunogenicity at enrolment, and weeks 4, 5, 8, 9, 20, 21, 22 (the primary endpoint), 24 and 44. Peripheral blood mononuclear cells (PBMC) will be collected at enrolment, and weeks 4, 8, 20, 21, 22, 24 and 44.

Adverse events will be assessed during the enrolment visit before and after immunisation and at every visit thereafter up to (and including) Week 22. Routine laboratory safety parameters will be collected at screening, enrolment, and weeks 1, 4, 5, 8, 9, 20, 21 and 22, and at any other visit if clinically indicated.

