9. WITHDRAWAL OF PARTICIPANTS

Withdrawal from the trial means stopping all further visits.

The reason(s) for withdrawal should be recorded on the Status CRF.

All participants are free to withdraw from the trial at any time, for any reason, without affecting their future medical care. An investigator may decide to withdraw a participant if the investigator deems that continuing might compromise participant wellbeing or interfere with the achievement of the trial's objectives.

Participants who are withdrawn due to an adverse event (AE) will be followed-up until the event has stabilised.

Withdrawn participants who have received any immunisations should be asked to undergo the procedures scheduled for the primary endpoint visit (Visit 10, week 22).

Policy for replacing withdrawals

Additional volunteers will be enrolled to replace early withdrawals or those who have discontinued their immunisations early, with the aim of having 24 subjects complete the study with no major protocol deviations. However, no more than 30 individuals in total will be exposed to the vaccine.

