10.4.2 Immunogenicity

10.4.2.1 Primary Immunogenicity Outcomes

All serum samples will be screened for antigen specific antibodies IgG (and IgA). The absolute levels of antibody in samples that are found to be positive will be determined using a standardised and quantitative ELISA developed in [name]'s laboratory at Imperial College London. In this sandwich capture ELISA, the Ab of interest is captured by the relevant target antigen and then detected using a labelled isotype specific secondary Ab. An estimate of the concentration of Ab in the sample is calculated by interpolation relative to a standard curve based on titration of purified human standards IgG or IgA captured by anti-human kappa/lambda-specific antibodies. The number of 'responders' in each assay will be presented by time-point and group as a proportion with 95% confidence interval. A 'responder' will be defined as a participant in whom a response was detected in at least one post treatment immunogenicity sample. Titres of antigen specific antibodies will be described by time-point and group, and compared using rank tests where appropriate. Although all samples will be processed, the analyses will be for the per-protocol population and conducted in [name]'s laboratory.

10.4.3

Exploratory Immunogenicity Outcomes

The proportion of individuals mounting a B cell response using frozen PBMC will be determined by B cell Elispot assay for antigen induced IgG production from antibody secreting cells (ASC's). CN54gp140 specific responses will be analysed as well as total IgG and compared between vaccine groups.

In addition vaccine induced T cell responses will be analysed by T cell Elispot assay for IFN- γ production on frozen PBMC samples and the proportion of individuals mounting a response quantified as SFU (spot forming units) compared between vaccine groups. These exploratory analyses will use descriptive statistics and will be conducted in [name]'s laboratory.

10.4.4

Safety Outcomes

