2.3. Analysis datasets

The statistical analysis will be conducted on randomised participants on both an Intention-to-Treat (ITT) and a Per-Protocol (PP) basis. This is a phase I trial concerned with both safety and efficacy, ITT provides estimates of effectiveness in a 'real-world' setting where participants missed doses or became lost-to-follow-up, PP estimates efficacy under ideal conditions.

- Intention-To-Treat (ITT) dataset: all participants randomised and given at least one immunisation in the trial.
- Per-Protocol (PP) dataset: all participants randomised and immunised with all scheduled immunisations, completing the trial with no major protocol deviations.

A safety analysis population is also defined as all participants receiving at least one dose of trial medication.

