4.5.2. Immunogenicity

Endpoint titres (concentration) of systemic CN54rgp140-specific IgG antibodies at 4 weeks from the final vaccinations will be described (mean and 95% C.I. – log10 scale - or median and IQR – original scale) by group for the responders, and compared using the Wilcoxon rank-sum test.

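### The protocol and SAP define the per-protocol set for primary immunogenicity differently: the protocol admits non-randomised replacements, the SAP does not, and neither defines trial completion

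*Protocol*

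**What the plan says.** **Analysis sets.** Protocol 10.4.1 describes replacement participants as people who were immunised without being randomised, and defines PP as "all participants randomised and non-randomised who were immunised with all scheduled immunisations, and who complete the trial". For primary immunogenicity, Protocol 10.4.2.1 states that "the analyses will be for the per-protocol population", places the work in the immunology laboratory, and plans rank tests between groups.

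SAP 2.3 states: "The statistical analysis will be conducted on randomised participants on both an Intention-to-Treat (ITT) and a Per-Protocol (PP) basis". Its PP set is "all participants randomised and immunised with all scheduled immunisations, completing the trial with no major protocol deviations". SAP 4.5.2 describes titres "by group for the responders, and compared using the Wilcoxon rank-sum test", without naming an analysis set. SAP section 4 says the trials unit does not hold the immunogenicity data and that they are analysed elsewhere.

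**Replacements.** Protocol section 9 replaces early withdrawals and early discontinuations, aiming for 24 completers, but "no more than 30 individuals in total will be exposed to the vaccine". For safety, Protocol 10.4.4 reports non-randomised participants separately. There is no matching rule for immunogenicity.

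**Completion.** Protocol 7.1 asks at least 11 visits of everyone, and Table 5 puts visit 11 at week 24. It adds that the 12th visit, "at Week 44, will only take place for participants known to have responded to the vaccine". Protocol 1.1.7 counts 12 visits for each subject, and Protocol 7.6 treats visit 12 as everyone's final visit. The primary immunogenicity endpoint is at week 22.

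**The concern.** The laboratory analyst has two incompatible PP definitions and no rule on which governs. Two different sets of people could each be reported as the per-protocol result.

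Followed as written, the protocol definition puts people who were not randomised into between-arm rank tests. The documents give no rule for assigning replacements to an arm, and Protocol 5.2 makes allocation known to clinical staff. Replacements also join later than those they replace.

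The completion condition is a separate weakness. Membership of a set used for a week-22 endpoint depends on attendance after week 22, and one of the later visits is offered only to responders. Protocol 2.2.4 links taking the strategy forward to whether electroporation affects the proportion making systemic IgG, so the responder proportion matters as well as the titre.

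**Working it through.** **1. The plan's own precision figures.** The Wilson interval has centre (p + z²/2n)/(1 + z²/n) and half-width z√(p(1−p)/n + z²/4n²)/(1 + z²/n), with z = 1.96.

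- 4/8: 0.50 ± 0.285, or 22–78%, as in SAP Table 3.
- 3/6: 0.50 ± 0.312, or 19–81%, as in SAP Table 3.

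Protocol Table 6 is labelled n=8, but its rows reproduce only at n=10 (no responders: 0–28% stated, 0–32% at n=8). I therefore use SAP Table 3. The label does not affect this point.

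**2. The two definitions side by side.**

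| Element | Protocol 10.4.1 | SAP 2.3 |
|---|---|---|
| Non-randomised replacements | included | excluded |
| All scheduled immunisations | required | required |
| Trial completion | required, undefined | required, undefined |
| Major deviations | not mentioned | must be absent |

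They conflict on two of the four elements.

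**3. Ceiling on replacements.** Assume 24 are randomised and immunised. The exposure cap leaves 30 − 24 = 6 replacements. That is 6/24 = 25% of a full set, or 6/8 = 75% of one arm if all fell there. The floor is zero.

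**4. What bias would require.** If k of 8 in one arm are replacements whose log titre differs by s standard deviations (SD), that arm's mean is biased by (k/8) × s. The documents give no value for s; I take 0.5 to 1.0 SD as an assumption. The last column is a simulation of the exact rank-sum test: 8 v 8, no true arm effect, everyone a responder, 4,000 runs, two-sided 5% level (also assumed).

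| k | Bias in arm mean (SD) | Rejection rate |
|---|---|---|
| 0 | 0 | 5.1–5.5% |
| 2 | 0.125–0.25 | 5.6–6.2% |
| 4 | 0.25–0.50 | 6.4–12% |
| 6 | 0.375–0.75 | 10–24% |

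The simulation error near 5% is √(0.05 × 0.95/4000) = 0.3 percentage points, so two replacements barely change the test. The effect is material only with many replacements in one arm and a sizeable difference.

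**5. Three readings of completion.**

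- *Week 24 for all:* no asymmetry between responders and non-responders.
- *Each participant's last scheduled visit:* everyone must reach week 24, and responders must also attend week 44. With true response p and week-44 loss d among responders, and no other loss, the PP proportion is p(1−d)/[p(1−d) + (1−p)]. For assumed d of 10%, 20% and 30%, p = 50% reads 47%, 44% and 41%, and p = 75% reads 73%, 71% and 68%. In one arm, losing two responders turns 6/8 (75%) into 4/6 (67%), or 4/8 (50%) into 2/6 (33%).
- *Visit 12 for all:* under Protocol 7.1 a non-responder has no visit 12, so none could qualify and the responder proportion would be 100% by construction.

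**6. Cost of a randomised-only set.** If all six replacements are used one for one, the set is 24 − 6 = 18: 6 per arm if losses are even, or 8/8/2 if all are in one arm. The interval around 50% widens from 22–78% to 19–81%. If everyone responds, the smallest two-sided exact rank-sum p, 2/C(n₁+n₂, n₁), goes from 2/12870 = 0.00016 (8 v 8) to 2/924 = 0.0022 (6 v 6) or 2/45 = 0.044 (8 v 2).

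**The case against.** Several points on the other side stand.

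- The primary population is named. Protocol 10.4.2.1 gives PP for immunogenicity, Protocol 10.4.4 gives ITT for safety, and Protocol 10.4 says the SAP will follow that summary. A reader might infer that no primary set exists. The narrower gap is which PP definition the laboratory applies.
- A reader might infer that the completion condition catches only responders. The documents do not support that. Anyone who misses visits up to week 24 can fail it. Only the week-44 step is specific to responders, and only on one reading. SAP 4.3 counts loss to follow-up as not reaching week 20, which suggests completion may not have been tied to week 44.
- The percentages in step 5 describe the responder proportion. SAP 4.5.2 compares titres among responders, where loss unrelated to titre and equal across arms costs precision but does not bias the comparison. The shifts also lie well inside the SAP Table 3 intervals at n=8 (41–93% for 6/8, 22–78% for 4/8).
- Six replacements is a ceiling, not a forecast.
- Any PP set is selected after randomisation, including the one proposed below.
- Protocol 2.2.1 calls the immunology mainly descriptive and unpowered.

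These limit the consequence. They do not remove the conflict: the definitions differ in current text, rank tests between arms are planned, and the protocol already keeps non-randomised participants apart for safety.

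**Conclusion.** The point holds as a conflict over who is in the primary immunogenicity set. The PP definitions disagree on non-randomised replacements and on major deviations, and nothing says which governs. Under the protocol version, 0 to 6 of 24 participants could be non-randomised, given 24 randomised and immunised. The comparison would then not be purely randomised.

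A reader might go further and conclude that the arm comparison is biased. The documents do not show that. Bias from replacements requires them to differ from the randomised participants; neither the direction nor the number used can be derived from the text.

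Trial completion is undefined. If it means each participant's last scheduled visit, a responder with a valid week-22 sample can be dropped for missing week 44. That lowers the responder proportion (75% would read 68–73% for an assumed 10–30% loss). It would bias the arm comparison only if the loss differs by arm or relates to titre.

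This should be corrected before the immunogenicity analysis.

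**What to change.** Put one PP definition in both documents: randomised participants, all four immunisations, evaluable week-22 serum, and one stated rule on major deviations, with no attendance required after week 22. Name it in SAP 4.5.2 as the set for primary immunogenicity and have the laboratory work from it.

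Report non-randomised replacements separately, outside the between-arm tests, as Protocol 10.4.4 does for safety.

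Two inconsistencies must be settled for the definition to work. The week-22 window is ±3 days in Protocol 7.1.2 and SAP 3.1.2 but ±7 days in SAP 4.3. The endpoint is 2 weeks after the final vaccination in Protocol 10.2.1.2 and SAP 3.1.2, but SAP 4.5.2 analyses 4 weeks.

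The cost is SAP wording and a short protocol clarification, plus some precision. If all six replacements are used one for one, the comparison set falls from 24 to 18, and an arm could be left with 2.

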10.4.2 Immunogenicity

10.4.2.1 Primary Immunogenicity Outcomes

All serum samples will be screened for antigen specific antibodies IgG (and IgA). The absolute levels of antibody in samples that are found to be positive will be determined using a standardised and quantitative ELISA developed in [name]'s laboratory at Imperial College London. In this sandwich capture ELISA, the Ab of interest is captured by the relevant target antigen and then detected using a labelled isotype specific secondary Ab. An estimate of the concentration of Ab in the sample is calculated by interpolation relative to a standard curve based on titration of purified human standards IgG or IgA captured by anti-human kappa/lambda-specific antibodies. The number of 'responders' in each assay will be presented by time-point and group as a proportion with 95% confidence interval. A 'responder' will be defined as a participant in whom a response was detected in at least one post treatment immunogenicity sample. Titres of antigen specific antibodies will be described by time-point and group, and compared using rank tests where appropriate. Although all samples will be processed, the analyses will be for the per-protocol population and conducted in [name]'s laboratory.

10.4.3

Exploratory Immunogenicity Outcomes

The proportion of individuals mounting a B cell response using frozen PBMC will be determined by B cell Elispot assay for antigen induced IgG production from antibody secreting cells (ASC's). CN54gp140 specific responses will be analysed as well as total IgG and compared between vaccine groups.

In addition vaccine induced T cell responses will be analysed by T cell Elispot assay for IFN- γ production on frozen PBMC samples and the proportion of individuals mounting a response quantified as SFU (spot forming units) compared between vaccine groups. These exploratory analyses will use descriptive statistics and will be conducted in [name]'s laboratory.

10.4.4

Safety Outcomes

The AEs for the randomised subjects will be coded by MRC CTU staff using MedDRA. If a participant reports the same event more than once then the worst severity and worst relationship to trial vaccine will be taken. Discrepancies between diary card and CRF reports will be queried by the monitor if unclear. It is assumed that the grade assigned by the clinician is more accurate, and this will be the grade reported in the ITT analysis tables, prepared by MRC CTU. If the diary card grade is worse, this will be foot noted.

All safety end-points will be graded by the Clinical Investigators.

Safety outcomes for the randomised participants will be reported overall with proportion and 95% confidence interval, and by group and time-point, and by relationship to study product, and method.

For the primary ITT analysis of safety endpoints (as defined in **section 10.2**), results will be expressed as a proportion with confidence interval, and groups compared using Fisher's exact test.

Safety outcomes for the non-randomised participants will be reported separately.

10.4.5

Tolerability Outcomes

The tolerability data from the questionnaires will not be part of the SAP or reported in the Clinical Study Report.

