10.2.1.2 Immunogenicity

- The magnitude of antigen specific systemic IgG antibody binding responses (µg/ml) 2 weeks after the final vaccination.

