1.3. Exploratory Objectives

To describe qualitative differences between the different methods of delivery in terms of changes from baseline in overall magnitude and functionality of antibody responses to the vaccines, and quantitative differences in cellular responses (CD4+ and CD8+ T cells).

To evaluate the tolerability of vaccination using the electroporation devices.

2. General Considerations

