3.1.2. Immunogenicity

The primary immunogenicity endpoint is the titre of systemic CN54rgp140-specific IgG antibodies measured 2 weeks \pm 3-day window after a participant's scheduled final vaccination (any exception to the 3-day window to be discussed by the TMG). Responses are measured using a semi-quantitative sandwich ELISA assay and defined as positive when exceeding mean OD at 450nm plus 3 SDs at a 1/100 dilution for a panel of serum samples obtained from 20 HIV negative volunteers. Samples deemed "response positive" are analysed further in a titration assay where samples are subsequently diluted to achieve at

least two OD at 450nm values that fall on the linear part of the relevant human IgG or IgA standard curve of known concentration. These values are interpolated automatically by the ELISA software (SoftMax Pro v 5.4) to give two extrapolated values in $\mu\text{g/ml}$. The mean of these 2 values is then reported as the “titre” of antigen specific IgG or IgA for response detected samples.

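### The only responder definition counts a positive in any post-treatment serum, so the set used for the primary titre comparison is not tied to week 22 or to the participant's own week-0 result.

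*Protocol*

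**What the plan says.** - **Endpoint.** Protocol 10.2.1.2 sets the primary immunogenicity endpoint as the magnitude of IgG binding "2 weeks after the final vaccination". Protocol 7.1 identifies this as week 22.
- **Responder.** Protocol 10.4.2.1 says a responder is "defined as a participant in whom a response was detected in at least one post treatment immunogenicity sample". The sentence before the titre description also promises that "The number of 'responders' in each assay will be presented by time-point and group as a proportion with 95% confidence interval".
- **Primary comparison.** SAP 4.5.2 describes titres "by group for the responders, and compared using the Wilcoxon rank-sum test". The SAP does not say who a responder is.
- **Positive sample.** SAP 3.1.2 calls a sample positive when its OD exceeds the mean plus 3 SD of a "panel of serum samples obtained from 20 HIV negative volunteers". Only positive samples are titrated.
- **Sampling.** Protocol 7.1 schedules immunogenicity serum at enrolment and at weeks 4, 5, 8, 9, 20, 21, 22, 24 and 44. The week-44 visit takes place only for participants already known to have responded. Table 5, footnote 5, puts immunisation after the visit's other procedures, so the week-20 serum precedes the boost.
- **Baseline.** SAP 1.3 includes "changes from baseline in overall magnitude and functionality of antibody responses to the vaccines" as an exploratory objective. Neither document uses the week-0 result to decide who is a responder.

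**The concern.** The trial asks what DNA priming does for the antibody response to the protein boost, measured at week 22. The responder rule answers a different question: was this person ever positive after the first dose?

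Three consequences follow if the rule is applied as written.

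1. The set compared in SAP 4.5.2 can include people with no titre at the endpoint visit. Neither document says whether they are dropped, set to zero or set to a floor value. With 8 per arm, one such person matters.
2. A response to DNA alone, or reactivity present before vaccination, counts as a response to the full regimen. DNA-only responses are plausible: Protocol 2.1.8.1 cites 70% seroconversion with the same plasmid backbone and similar Env inserts, given intramuscularly without electroporation.
3. Each participant has eight chances to cross the cut-off by noise instead of one.

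The proportion also matters beyond description. Protocol 2.2.4 says the strategy would be taken forward if electroporation affects the proportion making systemic IgG without compromising safety or tolerability.

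**Working it through.** **Plan's own figure.** The documents give no false-positive rate for the responder rule. The nearest stated figure is SAP Table 3 (Wilson 95% intervals), which reproduces at N=8: 0/8 gives 0-32.4%, 1/8 gives 2.2-47.1%, 4/8 gives 21.5-78.5% and 8/8 gives 67.6-100%. One misclassified person moves an arm's proportion by 1/8 = 12.5 points.

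**Which samples decide status.** There are nine post-treatment time points, less week 44 (known responders only), which leaves eight. Weeks 4, 5, 8, 9 and 20 precede the boost (five); weeks 21, 22 and 24 follow it (three).

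**The missing titre.** Take a participant positive at week 9 and negative at weeks 21, 22 and 24. Under Protocol 10.4.2.1 this is a responder. Under SAP 3.1.2 the post-boost sera are never titrated, so SAP 4.5.2 has no value to rank. SAP 4.5.2 names "CN54rgp140-specific IgG antibodies at 4 weeks from the final vaccinations" where SAP 3.1.2 says 2 weeks. That discrepancy needs its own correction, but this participant has no titre at either visit.

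**False-positive rate for one sample.** Assume normal ODs and participants exchangeable with the panel.
- Panel mean and SD known: 1 − Φ(3) = 0.135%.
- Both estimated from 20 sera: P(t with 19 df > 3/√(1 + 1/20)) = 0.43%.

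**Any of eight samples, treated as independent.** 1 − (1 − 0.0043)^8 = 3.4% per participant.

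**Simulation, normal ODs** (40,000 runs, one cut-off from 20 sera shared by all 24 participants):

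| Within-person correlation | Any of 8, per participant | At least one false responder in 24 |
|---|---|---|
| 0 | 3.3% | 37% |
| 0.5 | 2.4% | 32% |
| 0.8 | 1.5% | 24% |
| 0.95 | 0.9% | 16% |

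Week 22 alone gives about 0.43% per participant and about 9% for at least one in 24. The inflation is 0.9/0.43 ≈ 2 to 3.4/0.43 ≈ 8. The expected number of false responders among 24 is 0.21 to 0.80.

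**Simulation, log-normal ODs** (ln SD 0.5, same shared cut-off). One sample gives about 2.6%. Any of eight gives about 18%, 12%, 8% and 5% at correlations 0, 0.5, 0.8 and 0.95, an inflation of roughly 2- to 7-fold.

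**After the fix, normal ODs.** Week 22 positive with week 0 negative gives 0.43% (correlation 0) to 0.14% (correlation 0.95), or 0.10 to 0.03 expected among 24. Under any OD distribution the rate cannot exceed the single-sample rate, which is about 2.6% in the log-normal case.

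**The case against.** The best reply is that a per-visit reading is available. Protocol 10.4.2.1 promises counts by time-point, SAP 3.1.2 defines positivity sample by sample within the endpoint definition, and the later SAP never repeats the any-sample rule. On that reading a responder in SAP 4.5.2 is someone positive at that visit, and everyone in the comparison has a titre. This stands as a possible reading, so a reader should not infer that the definition rules out counts by time-point. But the any-sample sentence is the only participant-level definition in either document, and the two meanings give different sets.

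Nor should a reader infer that week-0 serum goes unused. All sera are screened, titres are described by time-point, and change from baseline is an exploratory objective. The gap is confined to classification. Protocol 4.2 excludes earlier recipients of HIV envelope vaccines, which lowers baseline reactivity without testing for it.

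It is also true that the primary endpoint is magnitude, and that Protocol 2.2.1 calls the immunology primarily descriptive and unpowered for group comparison. This limits the consequence. It does not settle who is in the comparison, and Protocol 2.2.4 still relies on the proportion.

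Finally, the two false-positive mechanisms partly offset each other. Stable non-specific binding means high within-person correlation, which shrinks the gain from repeated chances.

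**Conclusion.** The point holds as a definitional mismatch on the primary immunogenicity analysis. The ambiguity, the possible missing titres and the counting of pre-boost or pre-existing reactivity follow from the text and need no assumption about the assay.

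The false-positive part is right in direction, but its size is uncertain. Relative to week 22 alone the any-of-8 rule inflates the rate about 2- to 8-fold: roughly 0.9-3.4% per participant with normal ODs (under one expected among 24) and 5-18% with log-normal ODs. The distributions, the ln SD of 0.5, the correlation range of 0 to 0.95 and the exchangeability of participants with the panel are all assumptions.

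A reader might go further and take a 12% per-participant rate to 1 − (1 − 0.122)^8 = 65% for at least one false responder in an arm of 8. The documents do not support that figure. All participants are judged against one cut-off from the same panel, so they are not independent. With the shared cut-off, the log-normal case gives about 56% at the correlation of 0.5 that produces 12%, and 43% at 0.8. Normal ODs give 7-19%.

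**What to change.** In Protocol 10.4.2.1 and SAP 4.5.2:

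1. Define response separately at each time point, using the SAP 3.1.2 cut-off.
2. Define the primary responder as positive at week 22 with the participant's own week-0 serum negative by the same cut-off. If week 0 is positive, require a rise stated in advance, in screening OD or in titre. A general multiple of week 0 in µg/ml would not work, because negative samples are not titrated.
3. Use this set for the SAP 4.5.2 comparison and for the responder proportions.
4. Report positivity at any visit only as a secondary description.

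The cost is wording. Serum is already collected at both visits and all samples are screened, so no new samples or assays are needed. The downside is that responder percentages may be slightly lower.
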